8.2 Lung ultrasound

Lung ultrasound will be performed as described in Appendix 5. It is used to assess the state of lung ventilation (Appendix 5). A score from 0 to 3 (normal ventilation to complete loss of ventilation, respectively) is applied to each thoracic region. An overall lung aeration score out of 36 is calculated (Appendix 6). An ultrasound report is written (Appendix 7).

8.3 Diaphragm ultrasound

Ultrasound of the diaphragm will assess the excursion (mobility) and thickening of the diaphragm on the right and left. The procedure is described in Appendix 8. Each measurement will be repeated 3 times, the best one will be retained.

9 Conduct of the study

9.1 Pre-inclusion visit

9.1.1 Checking inclusion and non-inclusion criteria

When a patient is admitted to the Difficult-to-Wean Unit, one of the investigators checks the presence of inclusion criteria and the absence of non-inclusion criteria in the hospital admission report (HIR), during the admission visit and in the patient's computerised record.

9.1.2 Patient information and consent

When all the criteria allow the inclusion of the patient, the investigating physician informs the patient of the purpose of the study during a room visit. He provides the patient with all the information described in the information note (Appendix 9).

The state of consciousness of certain patients (under temporary sedation) when they are admitted to the Difficult-to-Wean Unit will not allow them to receive information related to the research and the collection of consent, and the information will be given to the person close to them who has been declared a trusted person (Appendix 10). As soon as the patient is awake, he or she will be informed of the research and asked for express oral consent to continue the research (Appendix 11). Decanulation only takes place when the patient is awake and compatible with good swallowing and satisfactory neuromuscular function.

In the event of a new ban on visits to hospital departments due to the health crisis, information and oral consent from the trusted support person will be given by telephone or videoconference.

9.2 Inclusion visit

All the data collected will be entered in the CRF..

9.2.1 Collection of consent

After sufficient time for reflection, the patient's or the patient's relative's express oral consent should be obtained. The date on which the patient or the patient's relative agreed to participate in the research is recorded in the computerised medical record, as is the date of withdrawal of participation, if any.

In the event that a patient's relative has given oral express consent, the patient will be informed of this research as soon as possible and asked for oral express consent for the possible continuation of the research (Appendix 11).

9.2.2 Data collection at inclusion

At the inclusion visit, the following data will be collected from the patient's computerised medical record, or directly from the patient or relative if data is missing:

- Age, sex (male/female), weight, height, body mass index (BMI);

Medical history: chronic heart disease (hypertension, coronary artery disease, dyslipidaemia, rhythm disorder), diabetes, chronic respiratory disease (Chronic Obstructive Pulmonary Disease (COPD), Sleep Apnoea Hypopnoea Syndrome (SAHOS), neurological disease, cancer, chronic renal failure, smoking (active, weaned, no), chronic alcoholism (yes, no);
 Data related to the initial ICU stay:

o Type of intensive care unit (medical, surgical, polyvalent) and type of institution (public, private non-profit, private);

o Reason for admission to intensive care: acute respiratory failure (ARF), ARF on chronic respiratory failure (CRF), cardiogenic shock, septic shock, haemorrhagic shock, polytrauma, post-operative, cardiorespiratory arrest (CRA), stroke, burns, pancreatitis, coma;

o IGS2 score on initial admission to the ICU.

- Number of failed extubations;
- Total duration of oro-tracheal intubation before tracheostomy (days);
- Number of VAPs (days);
- Performance of prone sessions (yes/no);
- If applicable, total duration of prone position (days);
- Use of ECMO support (veno-venous/arteriovenous/no);
- Tracheostomy performed (percutaneous/surgical/not);
- Resuscitation neuromyopathy (yes/no);

- Presence of BMR/BHR (yes/no);

- Limitation and discontinuation of active therapies (LATA) in the ICU (yes/no);

- Length of stay in intensive care (days);

- Type of tracheostomy cannula: uncuffed fenestrated, cuffed fenestrated, uncuffed non fenestrated;

- Cannula model (Shiley/Bivona/Trachoe/Other);

- Presence of mechanical ventilation (yes/no) and parameters:

o Mode: Controlled/PS/Other

o PS, PEEP, Vt, HR

o FiO2 (%)

- Biological check-up on admission within 48 hours of admission to DIFFICULT-TO-WEAN UNIT: haemoglobin, leucocytes, lymphocytes, neutrophils, troponin, renal function (urea, creatinine, GFR), metabolic function (calcium, magnesium, phosphate, TSH, cortisol at 8 hours, 25(OH)D) and inflammatory function (albumin, CRP);

- MRC score;

- Pulmonary ultrasound ;

- Diaphragmatic ultrasound;
- Confusional state by CAM-ICU (yes/no) (Appendix);
- Oral status (normal/moderate impairment/decay/no teeth);
- Vocal status (normal/minimal alteration/severe alteration/absence);
- Swallowing disorders by modified Cowling score (liquids/solids/both/not);
- Presence of undernutrition (severe/moderate/minimal/no);
- Presence of a nasogastric tube (yes/no);
- Presence of a percutaneous gastrostomy (yes/no);
- Oral feeding resumed (yes/no).

For data collection regarding the ICU hospitalisation prior to DIFFICULT-TO-WEAN UNIT hospitalisation, this will be done on the basis of hospitalisation reports and, if necessary, by requesting additional information through telephone calls to the ICU services or the attending physician.

9.3 End of research visit

The end-of-research visit will be carried out when the patient is discharged from the DIFFICULT-TO-WEAN UNIT. The necessary additional information will be collected from the patient's computerised medical record.

The variables collected are :

- Time to spontaneous ventilation (days);
- Time to 1st attempt at de-ventilation (days);
- Time to 24-hour de-ventilation (days);
- Time between 24-hour deventilation and successful final decanulation (days);
- Number of decanulations performed;
- Performance of a decanulation bronchial fibroscopy (yes/no) with abnormalities observed:
 - o pharyngeal oedema ;
 - o unilateral vocal cord paralysis;
 - o Bilateral vocal cord paralysis;
 - o unilateral arytenoid palsy
 - o bilateral arytenoid palsy;
 - o Tracheal ring fracture;
 - o No abnormality observed.
- Number of VAPs in DIFFICULT-TO-WEAN UNIT ;
- Total duration of antibiotic therapy (days) ;
- MRC score;
- Presence of undernutrition (severe/moderate/minimal/no);
- Presence of a nasogastric tube (yes/no);
- Presence of a percutaneous gastrostomy (yes/no);
- Oral feeding resumed (yes/no);
- Mode of discharge (return to intensive care, return home, death).

9.4 Bias control

In order to limit a possible measurement bias, the MRC score, the ultrasound measurements and the fibroscopic evaluation will be performed by one of the investigating physicians or physiotherapists, according to their respective competences, who are not part of the patient's care team.

9.5 Summary of all visits

| Données/actes | Pré- inclusion | Inclusion | Fin de recherche | | |
|--|-------------------|-----------|------------------|--|--|
| Recueil dans le CRH en réanimation, le DMI ou auprès du patient/proche | | | | | |
| Information du patient ou du | х | | | | |
| proche | Х | | | | |
| Consentement du patient ou du | | x | | | |
| proche | | ~ | | | |
| Données anthropométriques | | x | | | |
| (âge, poids, taille, sexe, IMC) | | | | | |
| Antécédents médicaux | | X | | | |
| Données liées au séjour initial en | | X | | | |
| réanimation | | | | | |
| Données liées à la ventilation : | | N N | | | |
| trachéotomie, VM (modes et | | X | | | |
| paramètres) | | | | | |
| Etapes sevrage ventilatoire | | | | | |
| (temps avant déventilation | | | X | | |
| journée, temps avant | | | | | |
| déventilation complète) Durée de séjour en SRPR | | | V | | |
| Modalités de sortie du SRPR | | | X X | | |
| | | | ^ | | |
| Mesures cliniques, physiologiqu | ies et biologiq | ues | | | |
| Bilan biologique (urée, créatinine, | | | | | |
| DFG, troponine, Hb, leucocytes, | | X | | | |
| PNN, lymphocytes, calcium, | | | | | |
| magnesium, phosphates | | | | | |
| Albumine, pré-albumine, CRP, | | X | | | |
| 25(OH)D, TSH, cortisol à 8h | | | | | |
| Scores fonctionnels | | | | | |
| MRC | | X | X | | |
| Hand-grip | | X | Х | | |
| Calorimétrie | | X | | | |
| Impédancemétrie :masse | | x | | | |
| maigre, masse grasse, dilution | | ^ | | | |
| Echographie | | | | | |
| Diaphragme | | X | X | | |
| Pulmonaire | | X | Х | | |
| Nutrition | | | | | |
| Alimentation PO, entérale par | | | V | | |
| GEP ou SNG | | X | X | | |
| Orthophonie | | I | | | |
| Troubles déglutition, état bucco | | v | | | |
| dentaire, voix, état confusionnel | | X | | | |

10 Statistics

10.1 Number of subjects needed

The calculation of the number of subjects required is based on the number of explanatory variables to be included in the multiple logistic regression model to determine the factors associated with successful decanulation. The "1 variable per 10 events" rule is applied. (23) We anticipate 6 variables to be included in the final multivariate predictive model, after selection of variables in univariate analysis, based on an estimated 60% success of decanulation (retrospective estimate on data available in the department), i.e. a necessary number of subjects of 100 patients.

10.2 General aspects

Descriptive statistics will be based on the use of means (± standard deviation) or medians (interquartile range) depending on the distribution of quantitative variables. Qualitative variables will be described in terms of numbers and percentages.

Univariate analyses will use the usual statistical tests after checking the distribution of the variables (Chi2 or Fisher's test; t-test, ANOVA or their non-parametric equivalents, Wilcoxon and Kruskal-Wallis tests). The Shapiro-Wilk test will be used to check whether the distribution of the data follows a normal distribution.

The multivariate analyses will be carried out by linear or multiple logistic regression models, depending on the type of variables.

The tests will be carried out with a significance level of 5%. The calculations will be made using R software (version 3.6.1, www.R-project.org) and Stata 15.0.

10.3 Main objective

Patients will be classified into 2 groups: success or failure of decanulation. The variables collected will be compared between the 2 groups by the appropriate tests according to the type of variables (quantitative or qualitative) and their distribution. The results of these comparisons will be used to select the variables showing a difference between the 2 groups (p < 0.20) for inclusion in the multivariate logistic regression. (24)(25)

The previously selected ultrasound variables will be included in the model predicting the success of decanulation. Multiple logistic regression with variable selection using the Akaike information criterion (AIC) method will be used. The presence of multicollinearity between variables will also be investigated and the variable eliminated if necessary.

11 Expected results in terms of scientific and professional advances

This study will determine the factors contributing to the success of decanulation in patients admitted to DIFFICULT-TO-WEAN UNIT after a prolonged ICU stay. The evaluation of these success factors will provide data that is still lacking due to the lack of literature in specialised post-resuscitation ventilatory weaning facilities.

This information may be useful in the post-resuscitation follow-up and in the prioritisation or not of early rehabilitation in these patients.

12 Expected benefits and risks for patients

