The failure rate of decanulation is between 2 and 25% (15)(16) with a poor prognosis in case of failure (17).

Thus, the determination of the success factors for decanulation of tracheostomised patients is a major challenge to select and optimise the management of these patients.

2 Hypothèse de recherche

The severity of the resuscitated patient, factors related to invasive ventilation, respiratory and extra-respiratory status are independent factors for successful decanulation.

3 Objectives

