4.1 Main outcome

Successful decanulation is defined as maintenance of spontaneous ventilation in the absence of recanulation, acute use of non-invasive ventilation (NIV) or death within 48 hours.

Factors potentially associated with successful decanulation will be collected prospectively:

- Severity factors related to the ICU stay:

o Total number of oro-tracheal intubations ;

o Number of days on mechanical ventilation;

o Curarisation or not with duration

o Whether or not prone sessions were performed with duration;

o Whether or not ECMO was used as a back-up;

o Number of pneumopathies acquired under mechanical ventilation;

o IGS2 ;

- Ventilatory factors :

o Number of failed extubations before tracheostomy in the ICU;

o Duration of mechanical ventilation before tracheostomy in the ICU (days);

o Type of tracheostomy used: percutaneous or surgical;

o Time to first attempt at Difficult-to-Wean Unit de-ventilation (days);

o Time to 24-hour at Difficult-to-Wean Unit de-ventilation (days);

o Time from 24-hour deventilation to successful DIFFICULT-TO-WEAN UNIT decanulation (days);

o Number of ventilator-associated lung diseases (VAPs) in at Difficult-to-Wean Unit;

- Respiratory factors:

o Ultrasound lung ventilation score on admission to at Difficult-to-Wean Unit;

o Diaphragmatic dysfunction on admission to at Difficult-to-Wean Unit;

o Bronchial fibroscopy abnormalities prior to decanulation;

- Extra-respiratory factors:

o Confusional state on admission to at Difficult-to-Wean Unit (CAM-ICU, Appendix 1);

o Existing swallowing disorders (assessed after 6 hours of ventilation) by the modified Cowling swallowing score (18);

o Oral status on admission to at Difficult-to-Wean Unit (normal, moderately impaired, dilapidated, no teeth);

o ICU-Acquired muscle weakness (MRC score) on admission to at Difficult-to-Wean Unit;

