4.2 Secondary outcomes

- Proportion of successful decanulation among all included patients (prevalence of successful decanulation);

- Proportion of successful weaning from IV among all included patients (prevalence of successful weaning from IV). Successful weaning from invasive ventilation is defined as the absence of invasive ventilation >48h ;

- The same factors potentially associated with successful weaning from IV will be collected as described in section 4.1.

- Collection of biological parameters within the first 48 hours of admission to Difficult-to-Wean Unit: haemoglobin, leukocytes, lymphocytes, neutrophils, troponin, renal function (urea, creatinine, GFR), metabolic function (calcium, magnesium, phosphate, TSH, cortisol at 8 hours, 25(OH)D) and inflammatory function (albumin, CRP);

- Ventilatory parameters on admission to Difficult-to-Wean Unit: ventilatory mode (VAC, VSAI), ventilatory settings (FiO2, PEP, AI, FR, Vt);

- Demographic characteristics of these patients during Difficult-to-Wean Unit hospitalisation: mortality, length of hospitalisation, duration of invasive ventilation.

- Nutritional assessment by evaluation of grip strength by Handgrip at admission and discharge from the Difficult-to-Wean Unit, by evaluation of the stage of sacral eschar at admission to the DIFFICULT-TO-WEAN UNIT, by measurement of resting energy expenditure by calorimetry at admission to the DIFFICULT-TO-WEAN UNIT and by measurement of lean mass, fat mass and dilution by impedancemetry at admission to the Difficult-to-Wean Unit.

5 Patient selection

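### Section 10.3 does not define decannulation failure, and by implication pools deaths and exits with the cannula with failed decannulations, so a predictor of death could be reported as a determinant of decannulation

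*Combined protocol and SAP*

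**What the plan says.** Section 10.3 gives the primary classification: "Patients will be classified into 2 groups: success or failure of decanulation". Variables that differ between the two groups at p < 0.20 enter a multiple logistic regression with AIC selection. There is no third class, no exclusion and no time-to-event method.

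Section 4.1 defines success only: "maintenance of spontaneous ventilation in the absence of recanulation, acute use of non-invasive ventilation (NIV) or death within 48 hours". Nothing says where to place a patient who dies before any decannulation, goes home with the cannula, or returns to intensive care still cannulated.

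Two places point to all included patients as the denominator. Section 4.2 lists "Proportion of successful decanulation among all included patients (prevalence of successful decanulation" as a secondary outcome. Section 10.1 reaches 100 patients "based on an estimated 60% success of decanulation".

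Section 1 says of attempted decannulation: "The failure rate of decanulation is between 2 and 25" per cent. Section 7.7 removes the cannula only after 48 hours plugged without a respiratory event and after satisfactory assessments.

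**The concern.** If every patient without a successful decannulation is a failure, the model gives the same outcome to three different courses: death before decannulation, leaving the unit with the cannula, and a decannulation that did not hold for 48 hours. A factor related only to the first can then separate the two groups without any bearing on decannulation.

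This touches the central hypothesis. Section 2 names patient severity first among the supposed independent factors, and section 4.1 lists IGS2, ECMO and the number of intubations, all plausible predictors of death. Sections 11 and 12.2 intend the results to inform early rehabilitation and therapeutic conduct. For those uses it matters whether a factor predicts survival or decannulation, and the one planned model cannot tell the two apart.

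**Working it through.** **1. The plan's sample size.** Section 10.1 gives 6 variables, 10 events per variable and 60% success.

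N = 6 × 10 / 0.60 = 100, the stated figure. The 60% is thus applied to everyone recruited, giving 60 successes and 40 others.

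**2. Make-up of the 40.** Let f be the failure rate per attempted decannulation (section 1: 2% to 25%). Attempted = 60/(1 − f); failed = attempted − 60; never decannulated = 100 − attempted.

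| f | Attempted | Failed | Never decannulated | Share of the 40 |
|---|---|---|---|---|
| 2% | 61.2 | 1.2 | 38.8 | 97% |
| 10% | 66.7 | 6.7 | 33.3 | 83% |
| 25% | 80.0 | 20.0 | 20.0 | 50% |

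How the never-decannulated patients split between deaths and exits with the cannula is not given.

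**3. A factor that acts only on death.** Assumptions: a binary factor present in half of 100 patients; overall mortality m (assumed, 5% to 30%); relative risk of death RR; all deaths counted as failures; the same success probability q among survivors in both groups.

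m0 = 2m/(1 + RR); m1 = RR × m0; q = 0.60/(1 − m); p0 = (1 − m0)q; p1 = (1 − m1)q.

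Example, m = 20% and RR = 2: m0 = 0.133, m1 = 0.267, q = 0.75, p0 = 0.65, p1 = 0.55. OR = (0.55/0.45)/(0.65/0.35) = 0.66.

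The table gives the pooled OR and the chance of passing p < 0.20 and p < 0.05 (two-sided two-proportion test, normal approximation, 50 per group). A null factor passes p < 0.20 in 20% of trials and p < 0.05 in 5%.

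| Mortality | RR 2: OR | p < 0.20 | p < 0.05 | RR 3: OR | p < 0.20 | p < 0.05 |
|---|---|---|---|---|---|---|
| 5% | 0.92 | 21% | 6% | 0.88 | 22% | 6% |
| 10% | 0.83 | 24% | 7% | 0.76 | 30% | 10% |
| 20% | 0.66 | 41% | 17% | 0.53 | 60% | 33% |
| 30% | 0.49 | 68% | 42% | 0.33 | 92% | 75% |

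Simulation with a continuous factor agrees (100 patients, about 60% success, competing exponential times). Doubling the death hazard per SD gave p < 0.05 in about 6, 11, 37 and 61% of trials at 5, 10, 20 and 30% deaths. A hazard ratio of 1.5 per SD gave about 6, 8, 17 and 28%.

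**4. Does separating the deaths help?** In step 3, removing the deaths leaves success probability q in both groups, so the OR is exactly 1.

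**5. Events for an added time-to-event model.** With successful decannulation as the event, 60/6 = 10 per variable. The protocol's own rule is met and N stays at 100. This counts only the six final variables, not the candidates screened.

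**The case against.** **Pooling is inferred.** Section 10.3 does not state it. The all-included denominator in section 4.2 belongs to a secondary outcome. The 48-hour definition presupposes a decannulation, and some candidate factors (pre-decannulation fibroscopy, time from 24-hour de-ventilation to decannulation) exist only for patients who reach that stage. A reading limited to attempted decannulations is therefore not excluded. It does not rescue the plan: 40% failure would contradict the cited 2-25%, and 61 to 80 attempts would yield only 1 to 20 failures, or 0.2 to 3.3 per variable for six variables.

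**The composite is legitimate.** A factor that raises mortality truly lowers the chance of leaving alive and decannulated, and section 10.3 describes a predictive model. The associations in the working are real associations with that composite, not false positives. This stands. The defect is that the outcome is undeclared and the result would be worded as a determinant of decannulation.

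**The size is not documented.** Unit mortality appears nowhere as a figure. A reader might infer that severity effects will certainly be misreported; near 5% mortality, or with a modest effect on death, they hardly would be.

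**Cox is not simply better.** A reader might infer that a Cox model should replace the logistic model because timing carries most of the information and power roughly doubles. That holds only if the factor changes the decannulation rate (about 70% power against 35% in simulation, 1.4-fold per SD). If it changes whether but not when decannulation succeeds, the order reverses (7-71% against about 77%). The documents do not say which applies. The two models also answer different questions.

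**Conclusion.** The point holds as a gap in definition with a real risk of misinterpretation. Failure is undefined, and the plan's own arithmetic implies that at least half of that class (about 20 to 39 of 40) would never have been decannulated. This rests on the all-included reading and on applying a literature failure range to the department's retrospective 60%.

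That a severity factor could be reported as a determinant of decannulation through its effect on death is a possibility whose size turns on assumed mortality and strength of effect. At 20-30% mortality with a doubled death risk, the pooled OR is 0.66 to 0.49 and the factor passes the p < 0.20 screen in 41-68% of trials, against 20% for a null factor. At 5% mortality the distortion is negligible.

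The documents do not support discarding the logistic model. They do support declaring what it estimates and adding analyses that separate survival from decannulation.

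**What to change.** In section 10.3:

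1. Keep the logistic model on all included patients, and declare its outcome as alive and successfully decannulated (48-hour criterion of section 4.1) versus all others.
2. Report the non-success group in three rows: died without successful decannulation, left with the cannula, decannulated but failed within 48 hours. State which row takes precedence for a patient who fits two, for example one who is recannulated and then leaves with the cannula.
3. Add a pre-specified cause-specific Cox model of time from unit admission to successful decannulation. Use factors known at admission, and treat death and exit with the cannula as competing events. Repeat the logistic model without the deaths.
4. Call a factor a determinant of decannulation, rather than of survival, only if it is consistent across these analyses. Judge this by direction and size with confidence intervals, because the model without deaths has fewer patients.

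**Cost.** No new patients or visits. Section 9.3 already collects the number of decannulations, the weaning times and the mode of discharge; sections 4.2 and 9.5 cover length of stay. Time to success is the sum of time to 24-hour de-ventilation and time from there to final decannulation. Cannula status at discharge is not listed and must be derived from these items. The price is a little more analysis, a proportional-hazards check and possibly more cautious conclusions.

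### Section 10.3 screens an open list of factors at p < 0.20 and reselects by AIC, with no internal validation or exploratory label, yet section 11 promises to determine the factors

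*Combined protocol and SAP*

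**What the plan says.** Protocol section 10.3 sets out the primary analysis in two selection steps. All collected variables are first tested one at a time: "The variables collected will be compared between the 2 groups by the appropriate tests according to the type of variables". Then: "The results of these comparisons will be used to select the variables showing a difference between the 2 groups (p < 0.20". The survivors enter a second step: "Multiple logistic regression with variable selection using the Akaike information criterion (AIC) method will be used". A multicollinearity check follows, with no threshold.

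Section 10.3 names no significance level for the final model. The only level is the general one in 10.2: "The tests will be carried out with a significance level of 5" (per cent), with no adjustment for the number of tests.

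The candidates are introduced in 4.1: "Factors potentially associated with successful decanulation will be collected prospectively". That list has 21 entries, but 10.3 does not restrict the screen to it, and 9.2.2 collects many further variables. One entry in 4.1 is "Time from 24-hour deventilation to successful DIFFICULT-TO-WEAN UNIT decanulation (days", collected under 9.3 as "Time between 24-hour deventilation and successful final decanulation (days". It has no value in a patient whose decanulation never succeeded.

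Section 10.1 sizes the study on the final model only: "We anticipate 6 variables to be included in the final multivariate predictive model, after selection of variables in univariate analysis". The available text contains no bootstrap, cross-validation, split sample, optimism correction or exploratory label. Section 2 hypothesises independent factors, and section 11 says that the study will determine them.

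**The concern.** Two separate problems arise.

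1. **Multiplicity.** Many candidates are each read at 5%, so the chance that at least one unrelated factor appears on the final list is far above 5%. This would be so without the screen or AIC.
2. **Selection.** The same 100 patients choose the model and estimate it. A factor tends to be kept when chance has made it look strong, so retained odds ratios run high.

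The list of factors is the primary result. Section 11 expects it to inform follow-up and the priority given to early rehabilitation. As planned, a reader would take a factor with p < 0.05 and its odds ratio at face value. Nothing reported would show how unstable the list is or how inflated the effects may be.

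**Working it through.** **The plan's own figure.** 10.1: 6 variables × 10 events ÷ 0.60 = 100 patients, which reproduces. That count covers the 6 final variables, not those screened. With 20 candidates, 100 patients give 60 ÷ 20 = 3.0 successes and 40 ÷ 20 = 2.0 failures per candidate.

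**How many candidates?** Section 4.1 lists 7 severity + 7 ventilatory + 3 respiratory + 4 extra-respiratory = 21. Removing the time to successful decanulation leaves 20. If patients who are never decanulated count as failures, the pre-decanulation fibroscopy and the two de-ventilation times may also be undefined for some of them: 20 − 3 = 17. So about 17 to 20 can be compared between groups. Section 9.2.2 holds about 68 items by count (5 anthropometric + 12 history + 4 ICU + 13 ICU stay and cannula + 7 ventilation + 16 biology + 11 clinical), many of which repeat 4.1.

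**Closed-form check.** For k independent null tests at 5%, P(at least one) = 1 − 0.95^k. For k = 20 this is 0.642; for k = 17 it is 0.582. Expected passes at p < 0.20 with k = 20: 20 × 0.20 = 4.0. For one coefficient, AIC retention corresponds to P(chi-square on 1 df > 2) = 0.157, which is looser than 5%.

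**Simulation of the planned procedure.** From the plan: n = 100, 60% success, screen at p < 0.20, AIC, 5%. Assumed: continuous candidates with a common correlation, t-test screen, backward AIC, two-sided Wald test in the final model, ultrasound variables treated like the rest, multicollinearity step omitted. All 20 candidates null, 5,000 simulated studies per column:

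| Assumed correlation | 0 | 0.3 | 0.5 |
|---|---|---|---|
| At least one factor at p < 0.05, screen + AIC | 67% | 60% | 46% |
| At least one at p < 0.05, plain univariate tests | 64% | 55% | 42% |

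A separate simulation of 2,000 studies per setting gave 67% and 59% at correlation 0 and 0.3, and 62% with 17 independent candidates. At correlation 0 with 20 candidates, about 4.0 passed the screen, 2.9 survived AIC and 1.15 were significant. The mean apparent AUC was 0.68 when the truth is 0.50. If 40 null candidates were screened, the rate at correlation 0 would be 91% to 92%.

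**Inflation of retained effects.** One true factor among 19 nulls, correlation 0, 4,000 studies per row:

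| True odds ratio per SD | Kept | Median odds ratio when kept | 95% interval coverage when kept |
|---|---|---|---|
| 1.3 | 41% | 1.64 | 0.912 |
| 1.5 | 66% | 1.74 | 0.948 |
| 2.0 | 95% | 2.18 | 0.965 |

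**Does uniform shrinkage help?** Multiplying coefficients by the bootstrap calibration slope (whole procedure resampled, 20 candidates, correlation 0) gave:

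- One true factor at 1.5: median 1.80 to 1.33; root mean square error (RMSE) of the log odds ratio 0.28 to 0.17.
- Six true factors at 1.6: median 1.91 to 1.42; RMSE 0.31 to 0.17.
- One true factor at 2.0: median 2.14 to 1.49, with RMSE rising from 0.28 to 0.33. A second run gave 2.04 to 1.45, with RMSE rising from 0.32 to 0.35.

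**The case against.** **This is ordinary exploratory practice.** Section 4.1 speaks only of potential association, and section 11 is expected-benefits prose that claims possible usefulness. That is fair as to tone. But nowhere is the analysis labelled exploratory, section 2 is firmly worded, and 10.1 and 10.3 also call the model predictive, which makes the absence of any validation a real gap.

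**Section 10.3 never says that the survivors are read at 5%.** This stands. The level is inferred from 10.2, and no other is offered. The inflation of retained odds ratios does not depend on that inference.

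**The simulation is idealised.** This also stands. Many 4.1 factors are binary or categorical; with ten binary candidates (assumed prevalence 5% to 50%) the rates are 62% and 56% at correlation 0 and 0.3. A global null is only a scenario, but with six true factors (odds ratio 1.6) among the 20, a false one still appears in 52% and 64% of studies at those correlations.

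A reader might also infer more than the documents support:

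- *That 20 candidates is a floor, or that 9.2.2 adds 68 more.* The usable number from 4.1 may be about 17. The 68 overlap with 4.1 and include the presence of ventilation, which the inclusion criteria fix.
- *That the screen and AIC cause the false-factor rate.* They add only 3 to 5 percentage points to plain testing in the table above.
- *That every retained interval fails.* For a single true factor, coverage stays between 0.91 and 0.97. It fell to 0.85 and 0.79 only with six true factors at correlation 0.3 and 0.5.
- *That shrunken odds ratios must replace the ordinary ones.* The stated aim is association, and shrinkage made a lone strong factor less accurate.

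**Conclusion.** The concern holds. Followed as written, the plan produces a primary list that is more likely than not to contain a false factor in the null scenario with 20 candidates at correlation 0 or 0.3 (67%, 60%), and close to half the time at 0.5 (46%). The rate is about 62% with 17 independent candidates. This is a multiplicity problem. Selection is a second and distinct problem that mainly affects weak factors: 1.3 is reported at about 1.64, 1.5 at about 1.74, and 2.0 at only about 2.18.

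These rates rest on assumed continuous, equally correlated candidates and on reading the final model at 5%. They show the size of the problem and are not predictions or bounds for this study. They do not show that the cohort is not worth running. The claim made for the factor list should match what the method can support.

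**What to change.** In section 10.3:

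(a) Fix the candidate list in advance as the 4.1 factors that are defined in both outcome groups. This caps the multiplicity but does not remove it.

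(b) Repeat the whole procedure (p < 0.20 screen and AIC) in at least 500 bootstrap resamples. Report inclusion frequencies, the bootstrap calibration slope, and optimism-corrected discrimination and calibration. This exposes the selection problem but does not lower the false-factor rate.

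(c) State that the factors identified are exploratory and that the 5% level is not claimed to hold for the list as a whole. This deals with the multiplicity that remains.

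Shrunken odds ratios may be shown beside the unshrunken ones as a sensitivity analysis, not as the required primary estimate.

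In section 11, say that the study will identify candidate factors rather than determine them.

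This is a cheap improvement: protocol wording and a short R script, with no extra patients or data and an unchanged objective. The downsides are a little more analysis and a more cautious conclusion.
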